Our central hypothesis is that our LIFT (+/- REAP) intervention will 1) improve adherence to recommended levels of exercise in end-stage liver disease 2) reduce pre-transplant frailty and 3) will improve pre- and post-transplant clinical outcomes.

STUDY ENDPOINTS:

Primary endpoints:

- Frailty (measured by Liver frailty index [LFI])
- Clinical outcomes: placement on LT waitlist, waitlist-mortality, post-transplant mortality, post-transplant disposition (acute rehabilitation, subacute rehabilitation center, home, etc), number of hospitalizations, duration of hospitalizations, liver related complications (ascites, hepatic encephalopathy, variceal bleeding, hepatorenal syndrome, hepatopulmonary syndrome, infections).
- Feasibility (measured by 8-question emailed survey)

[figure not shown]
Secondary endpoints:

- Endurance (measured by the 4-meter walk test).
- Patient adherence to the home exercise prescription (measured by daily diary counts of adherence to prescribed exercises, tracked on the TrueCoach application)
- Degree of hepatic encephalopathy (measured by List Sort Working Memory [LSWM] test and the Flanker Inhibitory Control and Attention [FICA])
- Patient-reported quality of life (measured by various PROMIS questionnaires)
- Feasibility/acceptability (measured by a study-specific questionnaire evaluating the acceptability and feasibility as reported by patients, providers and support staff)

STUDY INTERVENTION(S) / INVESTIGATIONAL AGENT(S):

Home exercise prescription (HEP) detailed below in study design.

PROCEDURES INVOLVED:

Recruitment for Quality of Life Assessment Study:

- A Northwestern Medicine Enterprise Data Warehouse (NMEDW) search will be used to identify all patients who have been seen in Transplant Evaluation Clinic and are currently being considered for liver transplantation or are already on the waitlist or have received a transplant.
- Alternatively, a list of the patients described above will be obtained from the transplant coordinator.

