 - This is performed in all patients in clinic, regardless of whether they consent for this study specifically.
 - Time: 5 minutes
 - Appendix F
- Physical therapy introduction
 - Setting: in clinic or at bedside if inpatient.
 - Provide equipment (weights, therabands, dynamometer, Truecoach smart phone application if not installed over the phone after consent was received)

- Demonstrate initial home exercise prescription, which will include a set of exercises to be done at home on a daily basis (cardio exercises, resistance exercises). These recommended exercises will be within standard of care.
- Time: 10-15 minutes

LIFT subgroup:

Follow up:

- *Text reminders (every day):*
 - An automated system will be used to generate and send daily text messages reminding patients to follow their HEP. Texts will be standardized and not contain any PHI.
- *Exercise data collection (continuously):*
 - Data continuously collected via TrueCoach smart phone application to document adherence to exercise regimen. If patients are unable to appropriately track adherence on the smart phone application, this data will be collected at weekly videoconference/telephone check-ins detailed below.
- *LFI calculation at home (every 4 weeks)*
 - A dynamometer will be given to each patient at time of enrollment. A video will be uploaded on the TrueCoach application demonstrating how to perform grip strength testing.
 - Balance testing and chair stands will be tested at home.
 - A team member will walk patients through each test via a videoconference call.
- *Patient-reported quality of life assessment at home (every 4 weeks, surveys emailed - Patients will be called by a team member who will walk the patient through the survey and record data over the phone)*
 - Tools: PROMIS surveys: Physical function – Short form 8c, Cognitive Function
 - Data collected via REDcap
- *Personality assessment at home (every 4 weeks, survey emailed - Patients will be called by a team member who will walk the patient through the survey and record data over the phone)*
 - Tool: Modified Midlife Development Inventory (MIDI) Personality Scale
 - Data collected via REDcap
- *Videoconference/telephone check-in (every 1 week):*
 - Performed by a member of the research team.
 - If patients are unable to track adherence to exercise regimen via TrueCoach application, the team member will document daily physical activity on this call.

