 - Patients will be asked to reflect on their experience with the HEP.
 - Discussion of barriers to engaging in HEP and how to overcome them.
 - Reflection on past experiences with obstacles outside of exercise that required patients to exert a lot of effort and how they were able to accomplish it.
 - How can you apply these strategies to your exercise goals?
 - Introduce action plans.
 - Discussion of industriousness and how to apply learned industriousness to exercise-related goal achievement.
 - Discuss building increments to get to exercise goals.
 - Identify the threshold for sustained effort where patients can still reach their goal.

- Instruct patients to document level of effort for each day of exercise and refer to them as needed. Patients will document effort in TrueCoach application via comments section.
 - 1 = no exertion at all
 - 2 = very light
 - 3 = somewhat hard (but still feels OK to continue)
 - 4 = very hard (strenuous)
 - 5 = maximal exertion
- *Text reminders (every day):*
 - An automated system will be used to generate and send daily text messages reminding patients to follow their HEP. Texts will be standardized and not contain any PHI.
- *Exercise data collection (continuously)*
 - Data continuously collected via TrueCoach application to document adherence to exercise regimen. If patients are unable to appropriately track adherence on application, this data will be collected at weekly videoconference/telephone check-ins detailed below.
- *LFI calculation at home (every 4 weeks)*
 - A dynamometer will be given to each patient at time of enrollment. A video will be uploaded on the TrueCoach application demonstrating how to perform grip strength testing.
 - Balance testing and chair stands will be tested at home.
 - A team member will walk patients through each test via a videoconference call.
- *Patient-reported quality of life assessment at home (every 4 weeks, surveys emailed - Patients will be called by a team member who will walk the patient through the survey and record data over the phone)*
 - Tools: PROMIS surveys: Physical function – Short form 8c, Cognitive Function
 - Data collected via REDcap
- *Personality assessment at home (every 4 weeks, survey emailed - Patients will be called by a team member who will walk the patient through the survey and record data over the phone)*
 - Tool: Modified Midlife Development Inventory (MIDI) Personality Scale
 - Data collected via REDcap

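### Both arms log exercise in TrueCoach, but only LIFT + REAP adds an effort entry there for each exercise day, so logging completeness may differ by arm and be read as a difference in adherence

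*Combined protocol and SAP*

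**What the plan says.** All references are to the combined protocol and SAP.

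- **Endpoint.** Study Endpoints lists adherence to the home exercise prescription as secondary, "measured by daily diary counts of adherence to prescribed exercises, tracked on the TrueCoach application". There is one definition for both arms.
- **Diary in both arms.** The LIFT schedule (Procedures Involved) has "Data continuously collected via TrueCoach smart phone application to document adherence to exercise regimen". The LIFT + REAP schedule has "Data continuously collected via TrueCoach application to document adherence to exercise regimen".
- **REAP only.** Under the REAP introduction: "Instruct patients to document level of effort for each day of exercise and refer to them as needed". The score runs from 1 to 5, and "Patients will document effort in TrueCoach application via comments section". The weekly check-in in this arm also has a REAP follow-up of 5 to 15 minutes, which covers the effort made in the past week.
- **Back-up.** In the LIFT schedule: "If patients are unable to appropriately track adherence on the smart phone application, this data will be collected at weekly videoconference/telephone check-ins detailed below". The LIFT + REAP schedule has an equivalent provision.
- **Hypothesis.** The first part of the central hypothesis (Background) is that LIFT, with or without REAP, will "improve adherence to recommended levels of exercise in end-stage liver disease". Background also gives better engagement and adherence as the reason for adding REAP.
- **Not stated.** The plan does not say how a day without an entry is scored, whether an effort comment counts toward adherence, or whether logging completeness will be compared between arms.

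**The concern.** A diary count rises for two reasons: the patient exercised more, or the patient recorded more of the exercise done. REAP is meant to act on the first, but its procedures may also act on the second. A patient who opens the app on each exercise day to enter an effort score, and discusses that effort every week, has an extra reason to tick off the session. The LIFT patient has the diary but not this prompt.

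Randomisation does not remove the problem, because any logging difference would arise after allocation and because of it. The count alone cannot separate the two explanations. At stake is the outcome closest to REAP's stated purpose: a higher count in LIFT + REAP could be reported as better adherence when part or all of it is better record-keeping.

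**Working it through.** **1. The arms side by side** (Procedures Involved)

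| Feature | LIFT | LIFT + REAP |
|---|---|---|
| TrueCoach exercise diary | yes | yes |
| Daily text reminder to exercise | yes | yes |
| Weekly check-in, progress reviewed | yes | yes |
| Call back-up if unable to track in the app | yes | yes |
| Effort score in TrueCoach for each exercise day | no | yes |
| Weekly review of past week's effort | no | yes |

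The last two rows differ, and the first of them takes place in the app that supplies the endpoint. The daily texts remind patients to follow the prescription; the plan does not say that they ask for logging. The safeguard for comparability given under Audio/Video Recording is the recording of calls, which does not reach app entries.

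**2. Illustration of size.** The plan gives no adherence rate, standard deviation or logging rate, so there is no figure of its own to reproduce. The inputs below are assumptions, apart from the total of 500.

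- True adherence: 60% of days in both arms, so no true difference.
- Between-patient SD of the recorded proportion: 0.30.
- Logging completeness: 85% in LIFT + REAP against 80%, 75% or 70% in LIFT.
- Days without an entry count as non-adherent.
- Comparison by a two-sided 5% test, normal approximation.
- Per-arm size: 50, 100 or 250. The total of 500 covers all groups (Participant Population(s)), including the Quality of Life study, and is not split. So 500 / 2 = 250 per arm is an upper limit.

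Spurious difference = true adherence × (completeness in LIFT + REAP − completeness in LIFT):

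- 0.60 × (0.85 − 0.80) = 0.03
- 0.60 × (0.85 − 0.75) = 0.06
- 0.60 × (0.85 − 0.70) = 0.09

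Standard error = 0.30 × √(2/n): 0.060 at n = 50, 0.0424 at n = 100, 0.0268 at n = 250.

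With z = difference / standard error, rejection probability = 1 − Φ(1.96 − z) + Φ(−1.96 − z).

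| Spurious difference | 50 per arm | 100 per arm | 250 per arm |
|---|---|---|---|
| 3 points | z = 0.50, 8% | z = 0.71, 11% | z = 1.12, 20% |
| 6 points | z = 1.00, 17% | z = 1.41, 29% | z = 2.24, 61% |
| 9 points | z = 1.50, 32% | z = 2.12, 56% | z = 3.35, 92% |

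The nominal rate is 5%, and equal logging returns 5%.

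**3. A milder case.** With true adherence of 40% and completeness of 80% against 85%, the spurious difference is 0.40 × 0.05 = 0.02. With SD 0.25 to 0.30, the test rejects 6–7% of the time at 50 per arm and 12–15% at 250. A small logging gap in a small trial therefore does little harm; a larger gap or a larger trial does more.

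**The case against.** Several points on the other side stand.

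- A reader might infer that only REAP patients enter anything in TrueCoach. They do not: both arms keep the same diary, and both have progress reviewed at the weekly check-in. What is exclusive to REAP is the added effort score and its review.
- A reader might also infer that effort comments are counted as adherence. Nothing says so. The endpoint counts prescribed exercises, and the score goes in a separate field. The bias needs a further step, that the comment prompts a check-off otherwise skipped. This is plausible but undocumented.
- The direction is not certain. A second daily task could tire patients and lower logging, which would hide a real benefit.
- Every logging gap above is assumed, the per-arm sizes are not in the plan, and the Statistical analysis section specifies tests for clinical endpoints without naming adherence.
- Adherence is secondary, and the first part of the hypothesis concerns LIFT with or without REAP, not REAP against LIFT. The Liver Frailty Index rests on performance tests and is not derived from app entries.

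One point stands only in part. The back-up in the exercise-data item speaks of patients who cannot track appropriately, which might be read to include incomplete loggers. The weekly check-in item drops that qualifier and refers simply to patients unable to track in the app. The text is ambiguous, so the back-up cannot be relied on to catch a capable patient who exercises and skips the entry.

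**Conclusion.** The concern holds as a risk of unequal measurement. The randomised intervention prompts use of the adherence tool in one arm, and nothing in the plan separates better logging from better adherence. It should be corrected, because adherence is the outcome REAP is most directly meant to change.

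The documents do not support saying that a bias exists, which way it runs or how large it is. On the assumptions shown (60% true adherence in both arms, SD 0.30, logging gap of 5 to 15 points in REAP's favour), the spurious difference is 3 to 9 points. The false-positive rate is about 8–32% at 50 per arm, 11–56% at 100 and 20–92% at 250. The last range is an upper limit, since not all 500 participants need be in the exercise trial. The point does not extend to the frailty endpoint.

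**What to change.** - **Same question to everyone.** Extend the existing weekly-call documentation to all participants in both arms: one fixed question on the number of exercise days in the past 7, asked before any REAP content and recorded in REDCap.
- **Keep the diary, and define it.** Count TrueCoach exercise check-offs only, not effort comments. State in advance how a day without an entry is scored. Treating all such days as unknown would not be a safe default, since many will be days without exercise.
- **Report logging completeness by arm**, comparing diary days with the weekly answer.
- **Restrict the claim.** Attribute an adherence effect to REAP only if both measures agree, with the meaning of agreement fixed before analysis.

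The cost is one question in a call both arms already receive, one REDCap field and some protocol wording. Seven-day recall is self-report, coarser than a daily diary, and less reliable in patients with encephalopathy, whom the trial includes. REAP patients who discuss effort each week may also come to answer differently; asking first limits this but does not abolish it. For these reasons the question supplements the diary and does not replace it.

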- Baseline clinical data will be collected at time of enrollment via the NMEDW and via chart review (will submit EDW exception). Data will include: Age, gender, race, ethnicity, body mass index (BMI), employment status, education, marital status, etiology of liver disease, complications of liver disease (ascites, hepatic encephalopathy, presence of esophageal/gastric varices, history of variceal bleeding, hepatorenal syndrome, hepatopulmonary syndrome), medical history (coronary artery disease, chronic kidney disease, dialysis dependence, hypertension, hyperlipidemia), and baseline laboratory data (platelets, serum sodium, serum creatinine, PT/INR, total bilirubin, albumin, calculated MELD) (Appendix A, B)
- Components of baseline session: (1) personality assessment (2) patient-reported quality of life assessment (3) hepatic encephalopathy assessment (4) frailty assessment, (5) physical therapy introduction.

- Personality assessment
 - Setting:
 - If consented over the phone prior to clinic visit, the personality survey will be emailed/texted to patients and completed over the telephone with a team member.
 - If consented in clinic visit or while admitted inpatient, the personality survey will be completed in clinic or at bedside with a team member.
 - Tool: Modified Midlife Development Inventory (MIDI) Personality Scale
 - Time: 38 questions, 3-5 minutes
 - Data collected via REDcap
 - Appendix C
- Patient-reported quality of life assessment (in clinic)
 - Setting:
 - If consented over the phone prior to clinic visit, the QOL survey will be emailed/texted to patients and completed over the telephone with a team member.
 - If consented in clinic visit or while admitted inpatient, the QOL survey will be completed in clinic or at bedside with a team member.
 - Tools: PROMIS surveys: Physical function – Short form 8c, Cognitive Function
 - Time: ~15 questions, 5 minutes
 - Data collected via REDcap
 - Appendix D
- Hepatic encephalopathy assessment
 - Setting: in clinic or at bedside if inpatient.
 - Tools: List Sort Working Memory (LSWM) test, the Flanker Inhibitory Control and Attention (FICA) test, Pattern Comparison Processing Speed Test administered on ipad and keyboard.
 - Time: 16 minutes (LSWM – 7 minutes, FICA – 3 minutes, PCPS – 3 minutes)
 - Appendix E
- Frailty assessment
 - Setting: in clinic or at bedside if inpatient.
 - Tools: Liver Frailty Index, 4-meter walk test
 - Balance testing
 - Repeat chair stands
 - Grip testing

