 - If patients have questions regarding exercise regimen, they will be contacted by a physical therapist.
 - Progress reviewed and exercise regimen potentially adjusted by a physical therapist based on data collected and patient experience.
- *Clinical data collection via NEDW and review of EMR (every 4 weeks)*
 - Number of hospitalizations, intensive care unit admissions, duration of hospitalizations, development of decompensating events (ascites, hepatic

encephalopathy, variceal bleeding), transplant status, type of LT (living donor LT, simultaneous liver-kidney), duration of hospital admission for LT, duration of ICU admission for LT, duration of intubation post-LT, post-transplant discharge disposition, date of death, cause of death, post-transplant complications (rejection, infection, biliary complications).

- *Clinic visits (every 3 months, same tools as noted above)*
 - Patient-reported quality of life assessment
 - Hepatic encephalopathy assessment
 - Frailty assessment, 4-meter walk test (standard of care)
 - Physical therapy in person update (standard of care)
 - Data collection via NMEDW extraction and chart review: Number of hospitalizations, intensive care unit admissions, duration of hospitalizations, development of decompensating events (ascites, hepatic encephalopathy, variceal bleeding), transplant status, type of LT (living donor LT, simultaneous liver-kidney), duration of hospital admission for LT, duration of ICU admission for LT, duration of intubation post-LT, post-transplant discharge disposition, date of death, cause of death, post-transplant complications (rejection, infection, biliary complications).
- Feasibility assessment (for those who remain in the study for at least 1 month or until receiving a liver transplant; surveys emailed)
 - Tool: 8 -question survey emailed to eligible subjects as noted above.
 - Data collected via REDCap.
 - Time: < 3 minutes
 - Appendix G

All participants who enroll for the PT intervention will be randomized (1:1) into the LIFT subgroup or the LIFT + REAP subgroup at 2 weeks after enrollment/baseline session. The LIFT subgroup will continue to follow up as detailed above. The LIFT + REAP subgroup will undergo Realistic Effort Action Planning (REAP), which is described below:

LIFT + REAP subgroup:

Follow up:

- *REAP introduction (2 weeks after enrollment, via telephone/videoconference, time: 30 minutes)*
 - Performed by a member of the research team.

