All telephone calls and videoconference calls between team members and patients will be recorded. Recording will be necessary to ensure standardization of follow up communications. This is critical in the pilot study to eliminate confounding factors between the LIFT and LIFT+REAP subgroups. Only IRB approved personnel will have access to the data. All data will be stored on FSM shared drive-accessed only by approved personnel. All data is accessed through password protected computer kept in locked offices. All patient identifiers will be stored in a separate password protected file. All recordings will be deleted within 3 years of study completion.

Retrospective Control group for those who enroll in the PT intervention study:

- A list of all patients who were evaluated for liver transplantation at Northwestern Memorial Hospital from January 1st 2018 through October 26th, 2020 will be drawn from the EDW.
- Baseline Clinical data will be collected via the EDW and via chart review. Data will include: Age, gender, race, ethnicity, body mass index (BMI), employment status, education, marital status, etiology of liver disease, complications of liver disease (ascites, hepatic encephalopathy, presence of esophageal/gastric varices, history of variceal bleeding, hepatorenal syndrome, hepatopulmonary syndrome), medical history (coronary artery disease, chronic kidney disease, dialysis dependence, hypertension, hyperlipidemia), and baseline laboratory data (platelets, serum sodium, serum creatinine, PT/INR, total bilirubin, albumin, calculated MELD). No data will be collected that is not already existing in the EMR at the date of IRB submission.
- Follow up data will be extracted retrospectively from the EDW and via chart review. Follow up data will include: Number of hospitalizations, intensive care unit admissions, duration of hospitalizations, duration of intensive care unit admission, development of decompensating

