- Baseline clinical data will be collected at time of enrollment via the NMEDW and via chart review. Data will include: Age, gender, race, ethnicity, body mass index (BMI), employment status, education, marital status, etiology of liver disease, complications of liver disease (ascites, hepatic encephalopathy, presence of esophageal/gastric varices, history of variceal bleeding, hepatorenal syndrome, hepatopulmonary syndrome), liver frailty index scores, Karnofsky Performance Status Scores, MELD scores, medical history (coronary artery disease, chronic kidney disease, dialysis dependence, hypertension, hyperlipidemia), and baseline laboratory data (platelets, serum sodium, serum creatinine, PT/INR, total bilirubin, albumin, calculated MELD) (Appendix A, B)
- Personality assessment
 - o Setting: Surveys will be administered via Redcap. Survey links will be emailed to patients. Reminder emails will be sent if no response is received. Surveys may be completed over the telephone with a team member if no response is received to email, or if the patient requires assistance.
 - o Tool: Modified Midlife Development Inventory (MIDI) Personality Scale
 - o Time: 38 questions, 3-5 minutes
 - o Appendix C

- Patient-reported quality of life assessment
 - Setting: See setting of personality assessment above.
 - Tools: PROMIS surveys: Global 10, Physical Function, Cognitive Function, Fatigue, Pain, Dyspnea, Spiritual Health and Social Activities.
 - Time: ~34 questions, 10 minutes
 - Appendix D

Follow up:

- Personality assessment
 - Setting: Surveys will be administered via Redcap. Survey links will be emailed to patients. Reminder emails will be sent if no response is received. Surveys may be completed over the telephone with a team member if no response is received to email, or if the patient requires assistance.
 - Tool: Modified Midlife Development Inventory (MIDI) Personality Scale
 - Time: 38 questions, 3-5 minutes
 - Appendix C
- *Patient-reported quality of life assessment at home (every 4 weeks)*
 - Setting: See setting of personality assessment above.
 - Tools: PROMIS surveys: Global 10, Physical Function, Cognitive Function, Fatigue, Pain, Dyspnea, Spiritual Health and Social Activities.
 - Time: ~34 questions, 10 minutes
 - Appendix D
- *Data collection via NEDW and review of EMR (every 4 weeks)*

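### Nothing stops a patient's REAP coach from also running that patient's home LFI and taking the PROMIS answers, and outcome assessment is not masked

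*Combined protocol and SAP*

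**What the plan says.** Study Endpoints lists frailty, measured by the LFI, as one of three groups of primary endpoints, beside clinical outcomes and feasibility. PROMIS quality of life is secondary. No time point is given for the LFI, and no rule says whether home or clinic readings are used.

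Under Procedures Involved, participants are randomised 1:1 to LIFT or LIFT + REAP two weeks after baseline. Both the REAP introduction and the weekly check-in, which contains the REAP follow-up, carry the note "Performed by a member of the research team".

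The 4-weekly home LFI is described identically for the two arms: "A team member will walk patients through each test via a videoconference call". Its home components are grip, balance and chair stands. The 4-weekly PROMIS survey is also worded alike in both arms: "Patients will be called by a team member who will walk the patient through the survey and record data over the phone".

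The Audio/Video Recording section has all calls recorded so that communication is standardised, and adds: "This is critical in the pilot study to eliminate confounding factors between the LIFT and LIFT+REAP subgroups". The LFI is also measured at clinic visits every 3 months.

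The protocol nowhere mentions blinding, masking, an independent assessor, or a division between those who deliver REAP and those who measure outcomes.

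**The concern.** Items such as "Repeat chair stands" and grip strength are performance tests. That their results respond to effort and encouragement is an inference from what the tests are, but a safe one. REAP is itself about effort: it discusses industriousness, sets a threshold for sustained effort and asks for a daily effort rating. If the coach who works on effort with a patient each week also talks that patient through the chair stands, the reading can shift without any change in frailty. PROMIS answers spoken to one's own coach are open to a similar pull.

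The randomised comparison is a behavioural addition to a package that both arms receive, so the true difference may be modest. A small measurement shift could then be taken for the effect being sought.

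**Working it through.** **Who does what after randomisation**

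| Activity | LIFT | LIFT + REAP |
|---|---|---|
| Weekly call | Research team member | Research team member, plus 5-15 minutes of REAP |
| REAP introduction | None | Research team member, 30 minutes |
| Home LFI, every 4 weeks | Team member by video | Team member by video |
| PROMIS, every 4 weeks | Team member by phone | Team member by phone |
| Clinic LFI, every 3 months | Yes | Yes |

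Randomisation is at 2 weeks and the first home LFI is due at 4 weeks, so every home LFI follows allocation. Whoever makes the weekly call to a REAP patient necessarily knows the arm. No rule stops that person from running the LFI and PROMIS calls for the same patient. The rows differ only in the REAP coaching, so that is the only difference between arms that can act through these calls.

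**Share of readings.** Over a full year on schedule there are 52/4 = 13 home and 12/3 = 4 clinic follow-up readings, so 13/17 = 76% are home tests. This counts readings. It is not a share of the primary comparison, because the protocol does not say which readings enter it.

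**Illustration of size.** The plan has no figure to reproduce: it states no alpha, power, effect size or LFI SD, and no separate number to be randomised. Inputs:

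- Two-sided 5% test (assumed), normal approximation to the planned t-test between arms.
- True effect zero; bias b = 0.1 or 0.2 SD in favour of REAP (assumed).
- n per arm = 50 or 125 (assumed), or 250, which is 500/2. The last is a ceiling, because the accrual table gives 500 for all groups and the Quality of Life Assessment Study falls under the same protocol.

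P(significant in favour of REAP) = 1 − Φ(1.96 − b·√(n/2))

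| n per arm | √(n/2) | b = 0.1 | b = 0.2 |
|---|---|---|---|
| 50 | 5.00 | 1 − Φ(1.46) = 7% | 1 − Φ(0.96) = 17% |
| 125 | 7.91 | 1 − Φ(1.17) = 12% | 1 − Φ(0.38) = 35% |
| 250 | 11.18 | 1 − Φ(0.84) = 20% | 1 − Φ(−0.28) = 61% |

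With b = 0 the probability is 2.5% at every n. For scale, 250 per arm detects (1.96 + 0.84)·√(2/250) = 0.25 SD with 80% power, so a bias of 0.1 to 0.2 SD would be a large part of the smallest effect that even the ceiling sample could reliably find.

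**The case against.** The other side has several fair points.

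- **The arms are treated alike.** A reader might infer that only REAP patients are assessed by people who coach them. The documents do not support that. LIFT patients have the same home LFI, the same PROMIS call and a weekly call from the same team. Only the increment from REAP can differ.
- **The overlap is shown for the team, not for individuals.** A reader might infer that the REAP coach does test his or her own patients. The protocol neither says so nor prevents it, and it does not state who enters the score.
- **The bias is assumed.** No document gives its size or direction, and the percentages only translate the assumption. This stands, and it limits how much weight they can carry.
- **The bias might look beyond repair once the data are in.** It is not wholly so. The clinic LFI is collected in both arms and avoids the home-call route. The recorded video tests could be re-scored by a masked rater, although that would not undo unequal encouragement during the test.
- **Why not simply make the clinic LFI primary?** At baseline it is routine: "This is performed in all patients in clinic, regardless of whether they consent for this study specifically". But clinic testing is not shown to be masked. Risks to Participants places physical therapists at clinic LFI testing, and physical therapists also review progress and adjust regimens. The clinic LFI therefore suits a sensitivity analysis better than it suits an unbiased standard.
- **Why not use self-completed PROMIS?** The Quality of Life Assessment Study sends the survey by email first: "Surveys may be completed over the telephone with a team member if no response is received to email, or if the patient requires assistance". The trial, however, includes patients with hepatic encephalopathy, and the protocol reports that electronic consent was impracticable in its study population. Self-completion first risks missing and mixed-mode data.
- **This is a pilot, and patients cannot be blinded to REAP.** True, but neither fact is a reason to let the coach be the assessor when a rota can prevent it.

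**Conclusion.** The point holds as a gap in design. Outcome assessment is unmasked, and nothing keeps a patient's REAP coach from running that patient's home LFI and PROMIS calls. Recording the calls supports standard scripts but does not hide the arm from the tester, and no masked review of the recordings is planned.

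The scope is limited. Among the primary endpoints, the LFI is the one that these team-led tests expose; PROMIS is secondary. Clinical outcomes such as death, transplant and hospitalisation come from the data warehouse and chart review, and are not exposed by this route.

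The illustrated false-positive rates in REAP's favour rest on an assumed bias of 0.1 to 0.2 SD, no true effect, a two-sided 5% test and an assumed number per arm. They show that a small shift would matter; they do not show that one will occur. The absence of any masking or separation of roles is certain from the text, whereas the size and direction of the resulting bias are unknown.

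**What to change.** Add to Procedures Involved, for both arms:

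1. The team member who runs and scores the home LFI and takes the PROMIS answers is never that patient's REAP coach. This person is not shown the allocation or the effort comments in TrueCoach. A rota within the existing team arranges this.
2. The assessor uses one fixed script with standard encouragement. The recordings already planned can be used to check adherence to it.
3. The mode of PROMIS completion is recorded for each survey.

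Add to Statistical analysis:

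4. The LFI comparison between arms, restricted to the 3-monthly clinic readings, is a pre-specified sensitivity analysis. The clinic LFI is done before the in-person physical therapy update, by a tester who is not shown the allocation where that is possible.

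The cost is protocol wording and scheduling effort, and no new visits are needed. Staffing is not described in the protocol, so the sponsor should confirm that the team is large enough for the rota. Masking will remain imperfect, because patients know whether they receive REAP and may say so. The clinic-only analysis uses fewer readings, and patients who miss clinic visits contribute less to it.
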